#### **7.1.4 Suspected Unexpected Serious Adverse Events - SUSAR's**

A SUSAR is any suspected unexpected adverse reaction related (or possibly related) to an IMP that is both unexpected and serious. In this case the event is not outlined in the Reference Safety Information (RSI) contained within the Summary of Product Characteristics (SmPC) for Carboplatin (section 4.8 of SmPC)

### **7.2 *Investigators Assessment***

It is the Chief/Principal Investigator's responsibility to assess and report all adverse events or reactions occurring from the time of patient registration until events that occur 30 days following the last dose of study medication or are thought to be related to study drug.

#### **Seriousness**

- Results in death
- Is life-threatening (defined as an event in which the patient or subject was at risk of death at the time of the event; it does not refer to an event which hypothetically might have caused death if it were more severe)
- Requires inpatient hospitalisation or prolongation of existing hospitalisation
- Results in persistent or significant disability/incapacity
- Is a congenital anomaly/birth defect
- Is an important medical event (defined as a medical event[s] that may not be immediately life-threatening or result in death or hospitalisation but may jeopardize the patient/subject or may require intervention (e.g., medical, surgical) to prevent one of the other serious outcomes listed in the definition above.) Examples of such events include, but are not limited to, intensive treatment in an emergency room or at home for allergic bronchospasm, blood dyscrasias, or convulsions that do not result in hospitalisation.

## **Causality**

The relationship or association of the study medication in causing or contributing to the AE will be characterized as either none, unlikely, possible or probable.

## **Expectedness**

- Expected
- Unexpected

## **Severity**

NCI CTCAE v4.0 criteria should be applied for assessing/reporting event severity/intensity: [http://ctep.cancer.gov/protocolDevelopment/electronic\\_applications/ctc.htm](http://ctep.cancer.gov/protocolDevelopment/electronic_applications/ctc.htm)

### ***7.3 Notification and reporting adverse events or reactions***

Patients will be monitored and questioned at every visit whilst on study treatment regarding the occurrence and nature of any adverse experiences. Any AE, including either observed or volunteered problems, complaints, or symptoms (whether or not associated with study medication) that begin at any time between the start of the first treatment and within 30 days after the administration of the last dose of study drug are to be recorded in the relevant section of the relevant CRF and sent to the CarPET Trials office within one month of the form being due.

### ***7.4 Notification and reporting of serious adverse events/SUSAR***

All AEs that are serious, unexpected, and definitely, probably, or possibly related to the study drug that occur during treatment or within 28 days of stopping treatment must be reported on the 'Serious Adverse Event Form' to the CarPET Trials Coordinator within 24 hours of the Investigator/Sub-Investigator becoming aware of the event.

**The SAE form must be signed off by the Principal Investigator (or medically qualified delegate) at the participating site and faxed or emailed to the Car-PET Coordinator on [name] or [[contact]](mailto:[contact]) together with relevant accompanying anonymised copies of treatment investigations.**

It will then be the responsibility of the Chief Investigator to inform the sponsor within 24 hours of becoming aware of the SAE. The relationship or association of the study medication in causing or contributing to the AE will be characterized as definitely, probably, possibly, or not related, as defined in Section 7.1.

### ***7.5 Notification and reporting of serious adverse events/SUSAR***

In accordance to The Medicines for Human Use (Clinical Trials) Regulation 2004 and its amendments, the prompt reporting of SUSAR's to relevant authorities lies with the sponsor. However, any SUSAR's which occur at any participating site should be reported to the Chief Investigator within 24 hours of the participating site learning of the event. It is the CI's responsibility to then report these to the sponsor. The sponsor will then submit these reports to the Competent Authority of the member state within **7 days** of receipt for fatal or life threatening SUSARs or within **15 days** for all other SUSARs.

Follow-up information by the sponsor will be sought within **8 days**. Each report should contain concise and clear information regarding the SUSAR.

## **7.6      Expected SAEs/SARs**

- Febrile neutropenia (requiring hospital admission)
- Neutropenia Grade 0-4 (asymptomatic)
- Mucositis Grade 0-4 (requiring hospital admission)
- Diarrhoea Grade 0-4 (requiring hospital admission)
- Thrombocytopenia Grade 0-4
- Renal Impairment (not requiring dialysis)
- Nausea and vomiting Grade 0-4 (requiring hospital admission)
- Neuropathy Grade 0-3
- Abnormal LFTs/Jaundice (resolving within 14 days of treatment)

As the IMP used in this study is licensed in the UK the ***expected*** SAE/SAR's are ***outlined*** in the ***current SmPC under undesirable effects*** and the expected SAE/SARs listed above should be recorded in the medical notes as well as the relevant CRF and sent to the CarPET Trials Office within one month of the form being due. **No SAE** forms regarding these expected SAE/SARs should be completed and sent to the sponsor.

## **7.7      *Pregnancy***

Patients must use adequate contraception whilst on the study and for at least 6 months after they stop receiving treatment as the adverse effects on reproduction are unknown. If a patient's partner becomes pregnant whilst enrolled in this CTIMP in which the foetus has been exposed to an investigational medicinal product, immediate reporting to the sponsor is required (within one working day of the PI/CI becoming aware of the event)

using a JRMO pregnancy template form. The CI/PI has the responsibility to ensure that the pregnancy form is completed and sent to the sponsor within the agreed timelines. Please state whether the patient can continue on the study or whether the patient has to be prematurely withdrawn from the study here.

The PI/CI also must follow up the pregnancy until delivery as well as monitoring the development of the newborn until birth. Any events that occur during this time that could be considered to be a SAE must be reported to the sponsor in line with section 7.6 utilising the sponsor SAE reporting form. Pregnant partners of participants will be asked to give consent for the release of this information to the study team.

### ***7.8 Urgent Safety Measures***

The CI may take urgent safety measures to ensure the safety and protection of the clinical trial subjects from any immediate hazard to their health and safety, this is defined in Regulation 30 of the Medicines for Human Use (Clinical Trials) Regulations 2004 [Statutory Instrument 2004/1031], as amended by Statutory Instrument 2006/1928. The measures should be taken immediately. In this instance, the approval of the Licensing Authority Approval prior to implementing these safety measures is not required. However, it is the responsibility of the CI to inform the sponsor, Main Research Ethics Committee (via telephone) and the MHRA (via telephone for discussion with the medical assessor at the clinical trials unit) of this event immediately.

The CI has an obligation to inform both the MHRA and Main Ethics Committee in writing within 3 days, in the form of a substantial amendment. The sponsor (JRMO) must be sent a copy of the correspondence with regards to this matter.

## **8 Annual Reports**

### **8.1 Development Safety update reports (DSURs) and Annual Progress Reports (APRs)**

The CI will submit APRs to the main REC and the sponsor on the anniversary date of obtaining a Favourable Opinion from the main REC using the National Research Ethics Service (NRES) template.

A DSUR will be submitted by the CI to the Sponsor, the relevant Ethics Committee and MHRA on the anniversary date of the “Notice of Acceptance” letter from the MHRA using the DSUR template provided by the sponsor. Subsequent DSUR reports will be due within 60 days of the anniversary date. The CI will carry out a risk benefit analysis of the IMPs encompassing all events having arisen on the trial.

## **9 Data handling and record keeping**

### **9.1 Confidentiality**

All information which is generated in the study will be kept strictly confidential. The researchers conducting the study will abide by the Data Protection Act 1998, and the rights the patient has under this act.

Once the patient consents to participate in the study their GP will be informed. Parts of the patients medical records and the data collected for the study will be reviewed by authorised personnel from Queen Mary University of London and also Bart's & The London NHS Trust who are the sponsors of this study. It may also be reviewed by representatives of regulatory authorities and other authorised personnel from the patient's trust, to check that the study is being carried out correctly. This is clearly stated on the consent form.

All of the above bodies have a duty of confidentiality to the patient as a research participant and nothing that could reveal their identity will be disclosed outside the research site. All data will be stored in a locked and dedicated data room only accessed by authorised personnel.

### **9.2 Essential Study documents**

All study related documents should be filed in the investigator's study site file. It should contain the protocol/amendments, Case Report and Query forms, Regulatory approvals with correspondence, sample patient information sheet and informed consent form, drug

records, staff curriculum vitae and delegation logs and other appropriate documents/ correspondence. The coordinating centre will inform the PI of any regulatory updates and forward on any relevant documentation. It is the participating sites responsibility to maintain this file and keep all staff records, including delegation logs up to date.

### **9.3 Case Report Forms**

The Case Report Form (CRF) must be completed legibly in black ink. Subjects are to be identified by initials, birth date, and subject number, if applicable. All requested information must be entered on the CRF in the spaces provided. If an item is not applicable it should be documented as such; do not leave a blank space. The completed CRF must be promptly reviewed, signed and dated by the Investigator or Sub-Investigator where applicable.

Any change or correction to a CRF should be made by striking through the incorrect entry with a single line (not obscuring the original entry) and then entering the correct information adjacent to the incorrect entry. The correction must be initialled and dated by the person making the corrections.

### **9.4 Record retention and archiving**

At the end of the trial, all essential documents as defined by ICH GCP (including CRFs, source documents, consent forms, laboratory results) will be securely archived by the coordinating and participating centres for a minimum of 20 years. During this time, documents must remain available for inspection by the Sponsor, auditors and members from regulatory bodies and the CI must be informed of the location of the archived material and the retrieval process. Following written authorisation from the Sponsor, arrangements for confidential destruction will then be made.

### **9.5 Compliance**

This study will be conducted in accordance with the principles of ICH Good Clinical Practice (GCP) as laid out in The Medicines for Human Use (Clinical Trials) Regulation 2004 and its amendments.

In addition, internal auditors and Competent Authority personnel will be allowed access to CRFs, source documents and other study files to evaluate the study. Audit reports will be kept confidential.

## **10 Governance Issues**

### ***10.1 Risk Assessment***

The sponsor together with the CI have assessed this study according to their risk assessment SOP 28.

### ***10.2 Summary Monitoring Plan***

On-Site monitoring will be performed on this trial. The trial coordinator/monitor should perform the first monitoring visit within 1 month of the first patient being enrolled at a site. Monitoring visits will be performed a minimum of twice a year during the recruitment and treatment period.

Sites that do not recruit any patients into a study will undergo on-site monitoring once a year.

The frequency of visits may change (increase or decrease) depending on the issues raised during the trial (death, SAE, audit or inspections, site not recruiting). Any decrease in monitoring at a site will be approved by a member of the CECM Management Team and the Sponsor.

### **Source Data Verification**

100 % SDV will be performed on informed consent.

100 % SDV will be performed on inclusion / exclusion criteria.

The following data points will undergo SDV for all patients

- Adverse events and toxicities levels;
- Metabolic response rate by FDG PET-CT scan and number of cycles required;
- Follow Up survival dates and progression disease dates for Progression Free Survival and Overall Survival.

100% SDV on all data points will be performed for a minimum of one patient per site or approximately 5% of all patients, whichever is greater.

Reasons for not performing on-site monitoring must be agreed with the CECM Management Team and the Sponsor and be fully documented in the TMF.

Original CRFs will be sent by post from site to the trial coordinator/monitor in a timely manner. Upon receipt of CRFs the trial coordinator/monitor will review for any obvious errors and data queries will be raised.

The following central facilities are utilised in this study:-

- Orchid tissue bank: Queen Mary University of London, Molecular Oncology Unit, [name].
- Central review of scans: University College London Hospital.

The following facility will undergo yearly monitoring visits for the duration of their participation in the study during the recruitment and treatment phase – once the follow-up phase is entered, its involvement with the trial will end. As such, monitoring will cease and the facility will be subject to a close-out visit:

- Orchid tissue bank.

The following facility will undergo 6 monthly monitoring visits for the duration of their participation in the study during the recruitment and treatment phase – once the follow-up phase is entered, its involvement with the trial will end. As such, monitoring will cease and the facility will be subject to a close-out visit:

- University College London Hospital - Institute of Nuclear Medicine

A summary of all monitoring activity for this study will be provided to the Sponsor at least every 6 months.

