### **1.3 Clinical data to date**

The Orchid Clinical Trials Group recently completed a study in metastatic seminoma using carboplatin AUC-10. Twenty patients received this dose of carboplatin for metastatic seminoma, with a median follow up of 29.4 months. Following the closure of the study a further 20 patients have received carboplatin AUC-10. In total 40 patients have been treated. There have been 2 relapses to date (5%), compared to the 18% relapse seen within the first 2 years of treatment of 28 patients who received AUC 7 or less with a median follow up of 135 months.

The relapsed patients were successfully salvaged using conventional chemotherapy. As nearly all relapses occur within 2 years of therapy, a 2 year progression-free survival is an appropriate endpoint for this phase II study.

In this most recent study, the protocol stipulated that all patients who were not in complete remission by day 21 of the first cycle would receive 4 rather than 3 cycles. This led to all those who essentially had greater than 2B disease requiring 4 cycles. This was probably unnecessary as most patients achieved a CR eventually – it just took time for the masses to shrink.

It is hoped that by substituting conventional CT for PET CT a greater proportion of patients will achieve a complete metabolic response and therefore the 4th cycle may be avoided in more patients. This will allow shortening of the treatment and reduction in the use of blood products as most of the blood transfusions required occur during the 4th cycle of carboplatin.

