### 5.3.3 Central review of PET-CT scans

There are currently no well validated metabolic response criteria for PET-CT in seminoma. Hence, we will use the criteria for assessment of response developed for the evaluation of lymphoma [6].

A Complete Response will be defined as **complete resolution** of all previously seen sites of nodal and metastatic disease. If residual sites of metastatic disease persist then the PET-CT will be used to evaluate metabolic activity.

Metabolic Complete Remission will be defined as the level of FDG uptake within the lesion that is no greater than normal mediastinal uptake these patients will receive 3 cycles in total. Lesions with uptake greater than the mediastinum will be viewed as non-complete

responders. The PET data will be viewed on standardised SUV (standardised uptake value) setting of between 0 and 5.0 and a visual comparison will be made to assess the degree of uptake within abnormal tissue [7]. These criteria will have a high probability of distinguishing true complete responders from partial responders. Contrast enhanced CTs will be evaluated via the standard response criteria (Appendix 4).

All PET-CT scans will be centrally reviewed at University College London Hospital. The results from the report will be used to determine the number of further treatment cycle's patients will require, following cycle 1. Copies of locally reported scans (where relevant) should be sent to the central reviewer via the secure NHS Image Exchange Portal system (IEP) for review by the central reviewer (please refer to appendix 7). Sending images via IEP will not apply to sites where patients are scanned at UCLH, however, sites must ensure that the proforma is completed and sent to remind the central reviewer. In addition to sending images via the secure IEP system, sites must email a copy of the Proforma Request form (see Appendix 5 and 6) that is appropriate to each site) to the central reviewer to indicate that an image has been sent via IEP.

The central reviewer will review the image and return the generated report within the appropriate timelines as stated in the table below (see Appendix 7);

All scans for central review to be sent to;

[name]

Consultant in Nuclear Medicine

Institute of Nuclear Medicine, T5

University College Hospital

[name],

[name]

[contact]

Proforma Request form to be emailed to: [[contact]](mailto:[contact]) and  
[[contact]](mailto:[contact])

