The central review reporting of the Baseline and Day 17-21 PET-CTs will take place **within 3 weeks** of the site either sending image or the patient having their scan done at UCLH. **The PET-CT scans must be received within this timeframe in order for the patient's response to treatment to be assessed and the decision on whether the patient receives 3 or 4 cycles can be made.**

Low dose attenuation correction CT will be performed at the time of the PET acquisition. Follow up conventional diagnostic CT scans from this point on should be received within two months of being performed.

Scan	Report to be received within
Baseline PET-CT & Baseline contrast enhanced CT	Within 3 wks of sending image/the PET scan (if done at UCLH)
Day 17-21	Within 3 wks of sending image/the PET scan (if done at UCLH)
Contrast enhanced CT performed post cycle 2 (if applicable)	Within 3 wks of sending image/the PET scan (if done at UCLH)
End of Treatment PET-CT or contrast enhanced CT	2 months
All other Contrast enhanced CTs as per follow up	2 months

If reports have not been received by the site within the timelines as detailed above, please follow the escalation process as detailed in Appendix 7.

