## **5.5 *Follow up***

- Patients will be followed up as part of the study for 2 years following completion of treatment.
- Outpatient follow up visits will be carried out **2 monthly** in the first year and **4 monthly** in the second year. Patients will then be followed at the PI's discretion and/or standard care.
- Details of disease progression must be documented on the CRF.
- Any further therapy for metastatic seminoma must be documented on the CRF.

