3.4 Study Variables

3.4.1 Primary and Secondary Variables

3.4.1.1 Primary Efficacy Variables

3.4.1.1.1 Progression-Free Survival (PFS)

PFS is defined as the time between the date of enrolment to first evidence of disease progression based on central review or death, whichever occurs first. For patients who have not died or experienced disease progression at the end of study, PFS will be censored on the last date the patient was known to be progression-free. Patients with no post-baseline tumour assessment will be censored at the date of enrolment plus 1 day. The PFS time will always be derived based on scan/assessment dates not visit dates.

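### The monitoring plan closes out the central imaging reader at the start of follow-up, in conflict with the imaging section and with the SAP's centrally reviewed PFS event

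*Protocol*

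**What the plan says.** **Monitoring plan.** Protocol 10.2 (Source Data Verification) lists UCLH as the facility for central review of scans. Its Institute of Nuclear Medicine is to be monitored every 6 months during recruitment and treatment; then "once the follow-up phase is entered, its involvement with the trial will end", monitoring ceases and there is a close-out visit. The same sentence is used for the tissue bank. The follow-up phase is not defined.

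**Imaging section.** Protocol 5.3.3 says "The central reviewer will review the image and return the generated report within the appropriate timelines as stated in the table below". That table has a row for "All other Contrast enhanced CTs as per follow up", with reports due in 2 months, and the text above it adds: "Follow up conventional diagnostic CT scans from this point on should be received within two months of being performed".

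**Endpoint.** SAP 3.4.1.1.1 runs PFS from enrolment to "first evidence of disease progression based on central review or death, whichever occurs first". For patients without an event at the end of study, "PFS will be censored on the last date the patient was known to be progression-free". Protocol 11.5, which gives the primary analysis, does not mention central review.

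**Local data.** Protocol 5.5 requires that "Details of disease progression must be documented on the CRF", and 10.2 has progression dates source-verified for all patients. Neither document says how a progression with a local read but no central read is to be classified.

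**The concern.** Treatment is three or four 3-week cycles, so 9 to 12 weeks. The endpoint is at 2 years, with CTs at 1 and 2 years after therapy for complete responders (Protocol 5.3.2). Protocol 1.3 justifies the endpoint with the statement "As nearly all relapses occur within 2 years of therapy", so most of the period at risk is follow-up. For the tissue bank the close-out sentence does no harm, because research blood is taken only before treatment. For the imaging reader it removes the assessor on whom the SAP's event definition depends.

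Two outcomes are possible, neither intended:

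- **10.2 is followed.** A progression seen locally after close-out has no central read and does not meet the SAP definition. The patient drops out of the event count, which pushes the Kaplan-Meier estimate up.
- **5.3.3 is followed.** The reader goes on reporting endpoint scans after its close-out visit, without the 6-monthly monitoring that the plan provides.

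If sites substitute local reads informally, early progressions are judged centrally and late ones locally, under one nominal definition.

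**Working it through.** **1. The plan's own design.** Inputs from Protocol 11.2.1 and 11.5: unacceptable rate 75%, target rate 90%, one-sided 5%, power 80%, success if at least 39 of the first 45 are progression-free at 2 years. Exact binomial:

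- P(X ≥ 39 | n = 45, p = 0.75) = 0.0446
- P(X ≥ 39 | n = 45, p = 0.90) = 0.841
- 45 is the smallest n that meets both limits, and 45/0.9 = 50 to recruit.

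The design reproduces.

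**2. Assumptions for the illustration.** The documents give no figure for unread progressions. I assume:

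- even accrual (the 48 months is from Protocol 11.1.3);
- close-out when the last patient ends treatment, 48 months plus up to 12 weeks, so about month 51;
- relapses spread evenly over 24 months from enrolment;
- every relapse after month 51 unread and counted as progression-free.

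**3. Share of progressions unread.** If the analysed patients enrol evenly over A months, the longest stretch of any 24-month window beyond close-out is m = A + 24 − 51, and the unread share is f = m² / (2 × 24 × A).

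- First 45 of 50: A = 48 × 45/50 = 43.2, m = 16.2, f = 16.2²/(48 × 43.2) = 12.7%.
- The 45 span all 48 months (drop-outs spread through accrual): m = 21, f = 21²/(48 × 48) = 19.1%. Here 21/48 = 44% of patients are still inside their window at close-out.

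**4. Effect on the decision rule at true PFS 75%.** Apparent PFS = 1 − 0.25 × (1 − f).

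| Case | f | Apparent PFS | P(at least 39/45) |
|---|---|---|---|
| All progressions read | 0 | 75.0% | 4.5% |
| Front-loaded relapses (mean about 9 months), 45 over 48 months | 9.8% | 77.5% | about 9% |
| Even relapses, first 45 of 50 | 12.7% | 78.2% | about 11% |
| Even relapses, 45 over 48 months | 19.1% | 79.8% | about 17% |

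In the last row 0.25 × 45 = 11.25 failures are expected, of which 11.25 × 0.191 = 2.1 go uncounted.

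**5. Censoring instead of counting as success.** A patient with a documented local relapse is not known to be progression-free after it, so the SAP rule would censor him before 2 years.

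- *39/45 count:* if a patient censored early is not accepted as one of the 39, the chance of passing stays at 4.5%.
- *Kaplan-Meier estimate:* it is still biased upward. Simulation under the last-row assumptions gives about 79.5%, against 79.8% when unread relapses are counted as progression-free.

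The documents do not say how censored patients enter the 39/45 count.

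**The case against.** The strongest reply is that Protocol 5.3.3 is the operative imaging section and does provide for central reads in follow-up, while 10.2 is a monitoring summary that repeats its tissue-bank sentence. Progression is also recorded on the CRF and source-verified, the only analysis that decides the trial comes at the end of the study, and a late central read could be obtained before then. Deaths count whatever happens to the scans. On this view the data are captured and nothing need be lost.

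Much of this stands. A reader might infer that central review simply stops at follow-up and that 2-year PFS is therefore inflated. The documents do not support that: they contradict themselves, and inflation needs 10.2 to prevail over 5.3.3, no later central read, and local progressions to be disregarded. Nor is the restriction to central review common to both documents; it is the SAP's alone.

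A reader might also take the follow-up phase patient by patient, so that nearly every post-treatment progression is lost. But 10.2 sets that phase against the recruitment and treatment phase and ties it to a single close-out visit to the facility, which points to a trial-level date.

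The reply does not remove the contradiction, and it supplies no rule for a progression that has only a local read. If 5.3.3 prevails, the endpoint reader still works unmonitored after close-out.

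**Conclusion.** Wrong as written: Protocol 10.2, Protocol 5.3.3 and SAP 3.4.1.1.1 cannot all be followed, and the conflict touches the primary endpoint. Confidence in the contradiction is high.

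The bias is conditional. If progressions after close-out go unread and uncounted, the Kaplan-Meier 2-year PFS moves upward. The 11-17% false-positive chance (about 9% with front-loaded relapses) is an illustration that rests on even accrual, close-out near month 51 and unread relapses counted among the 39. The decision rule keeps its 4.5% if patients censored before 2 years are not accepted as successes. The plan should be corrected before the analysis, but the point does not undermine the design.

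**What to change.** **Protocol 10.2.** Keep the UCLH central review facility active and on its 6-monthly monitoring until the last patient's 2-year scan has been centrally reported, and move its close-out visit to after that. Define the follow-up phase as a trial-level date. The tissue-bank sentence can stay.

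**SAP 3.4.1.1.1.** Align the event definition with Protocol 11.5. State that a locally documented progression with no central read counts as a PFS event at the local scan date in the primary 39/45 analysis, and add a sensitivity analysis that uses central reads only.

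**Cost.** Short wording changes in each document and a few more monitoring visits to a facility that 5.3.3 already expects to report follow-up scans. The sample size, the 39/45 threshold and patient care do not change.
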